# **11.0** Statistical Analysis of the Study

The primary endpoint of the trial is a renal function as assessed by 24 hour creatinine clearance.

We will compare creatinine clearance between the two arms of the study using a t-test. We expect that due to randomization there will be no differences in baseline characteristics of the two groups, so no multivariate analyses are planned. However, if we find significant difference between the two groups in such variables as demographics or disease characteristics, we will control for these variables in a linear regression analysis. In addition, we will also explore the use of nonparametric tests (i.e. Mann-Whitney U test for renal function) because of the relatively small sample size.

Secondary endpoints will also be tested using univariate statistical tests. The presence of acute rejection will be compared between study arms using chi-square tests. We will also fit nonparametric survival models to the time to acute rejection to determine whether rejection occurs earlier or later between study arms. Patient and graft survival will be modeled using Kaplan-Meier curves, with comparisons made between arms using the log rank test. To study the effect of donor and recipient genotype testing on postoperative renal function we will study the interaction between treatment arm and presence of CYP3A and P-gp SNPs on creatinine clearance. This will be done using a one-way analysis of variance with main effects for treatment and SNPs, and interaction terms between treatment and the SNPs.

Safety endpoints are all binary indicators (discontinuation, change of therapy, hyperlipidemia, etc.). All of these safety endpoints will be compared between treatment arms using chi-square tests.

Amendment 6Page 13 of 18

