#### Tests at above evaluation schedule:

- a. Renal function as assessed by the iothalamate clearance test starting at Baseline visit.
- b. Renal Function as assessed by serum creatinine, by Cockcroft-Gault formula mL/min, and 24 hour urine collection for creatinine clearance and urinary protein level starting at Baseline visit.
- c. Liver Recipient blood sample for genotype testing.
- d. Testosterone levels

The genetic tests will involve TaqMan real-time PCR of extracted DNA, and subsequent identification of alleles associated with investigated polymorphic SNP by means of allele-specific 5' nuclease assay, using the pre-developed assay and Custom TaqMan® SNP Genotyping reagents for allelic discrimination by TaqMan real-time PCR on AbiPrism 7900HT Sequence Detection System (Applied Biosystems, Foster City, CA). The above will involve following genes and polymorphisms: CYP3A5

#### Amendment 6Page 8 of 18

IRB # 38115 Version: December 28, 2018

gene: 6986 A>G (alleles \*1 and \*3) and ABCB1 (MDR1) exon26 (3435C>T) and exon21 (2677G>T/A).

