For all statistical analyses we will define significance as p-values less than 0.05. If multiple comparisons are required (for example, to study the same variable at difference time points) then we will adjust the p-values using a Bonferroni correction.

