#### Sample size and power:

The study was powered to measure significant improvements in renal function. To estimate the required sample size we assumed that the estimated glomerular filtration rate (eGFR) would improve from 34 mL/min/1.73 m^2 to 43 mL/min/1.73 m^2 as reported in a recent study by Fairbanks et al [29]. This is a conservative estimate since the renal sparing effects of everolimus are larger than those of sirolimus. A sample size of 12 in each group will have 80% power to detect a difference in means of -9.0 (the difference between a Group 1 mean of 34.0 and a Group 2 mean of 43.0) assuming that the common standard deviation is 7.5 using a two group t-test with a 0.050 two-sided significance level. Fairbanks did not report standard deviations for eGFR, however, a simulation study suggests that the standard deviation at baseline was 7.5, and the standard deviation following conversion was 16. We therefore, considered the sample size requirement for a range of standard deviations, shown in the Figure below. If the common standard deviation was 16, then 51 patients per group would be required to detect a significant difference of 9.0 with 80% power. This sample size may not be feasible for a pilot study such as this. However, 12 per group is feasible and can be justified by the lower limit of standard deviation reported in Fairbanks.

IRB # 38115 Version: December 28, 2018

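### Primary comparison ignores baseline creatinine clearance unless a baseline test is significant; a pre-specified ANCOVA would usually be more powerful and would remove the effect of chance imbalance

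*Combined protocol and SAP*

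**What the plan says.** Section 11.0 sets the endpoint: "The primary endpoint of the trial is a renal function as assessed by 24 hour creatinine clearance". The analysis follows: "We will compare creatinine clearance between the two arms of the study using a t-test". Because randomization is expected to balance the arms, the section continues "so no multivariate analyses are planned". The one exception is a linear regression used "if we find significant difference between the two groups in such variables as demographics or disease characteristics, we will control for these variables". The significance level is given near the end of the section: "For all statistical analyses we will define significance as p-values less than 0.05".

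The list of tests under the evaluation schedule in Section 6.0 includes "24 hour urine collection for creatinine clearance and urinary protein level starting at Baseline visit", so the baseline value of the primary endpoint will exist for each patient. Section 11.0 does not name it as a covariate, and does not say whether the t-test is on the follow-up value or on change.

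The sample size paragraph works with raw group means, "a difference in means of -9.0 (the difference between a Group 1 mean of 34.0 and a Group 2 mean of 43.0"), with a common SD of 7.5, "using a two group t-test with a 0.050 two-sided significance level". It takes no credit for a baseline covariate.

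**The concern.** Randomization balances baseline clearance only on average. With 24 patients, a moderate imbalance in the variable most likely to predict the outcome is common, and an unadjusted comparison carries part of it into the estimated effect.

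The adjust-if-significant rule is a poor safeguard for three reasons:

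- A baseline test at this size detects only very large differences.
- Significance of a baseline difference says nothing about whether the variable predicts outcome.
- The list of candidate variables is open, so in an open-label trial the primary model is not settled until the baseline comparisons have been seen.

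At stake are power the trial could have at no extra cost, and an estimate that can be off by a material part of the 9 mL/min target when the arms start unequal.

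**Working it through.** **Inputs from the documents.** 12 per arm, two-sided alpha 0.05, difference 9, SD 7.5 (planned) or 16 (the alternative in the sample size paragraph). These SDs are for eGFR; their use for 24-hour clearance is the plan's own assumption.

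**Input not in the documents.** The baseline-to-follow-up correlation r, shown here from 0 to 0.7. Data are taken as normal, with equal SD at baseline and follow-up unless stated.

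**1. The plan's figures.** Exact two-sample t-test (noncentral t): 12 per arm at SD 7.5 gives 80.2% power, and 51 per arm at SD 16 gives 80.3%. Both stated sizes reproduce. At 12 per arm and SD 16, power is 26.1%.

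**2. When the rule fires.** The difference needed for p < 0.05 is t(0.975, 22) × √(2/12) × SD = 2.074 × 0.408 × SD = 0.847 SD. That is 6.35 mL/min at SD 7.5 (71% of 9) and 13.55 at SD 16 (more than 9). For a single variable the rule fires in about 5% of trials.

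**3. How often imbalance goes unadjusted.** P(|imbalance| > 0.5 SD) = 2 × [1 − Φ(0.5/0.408)] = 22%. By simulation, about 17% of all trials exceed 0.5 SD without reaching significance.

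**4. Shift in the estimate from a 0.5-SD imbalance.** Shift = r × 0.5 × SD, at r = 0.3 / 0.5 / 0.7:

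- SD 7.5: 1.1 / 1.9 / 2.6 mL/min, or 13% / 21% / 29% of 9.
- SD 16: 2.4 / 4.0 / 5.6 mL/min, or 27% / 44% / 62% of 9.

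**5. Power for a difference of 9.** ANCOVA uses residual SD = SD × √(1 − r²), 21 degrees of freedom, and variance factor 1 + t₀²/22 averaged over the baseline t statistic t₀ (mean factor 1 + 1/20 = 1.05). The plan's rule, applied to baseline clearance, was simulated with 200,000 trials per setting.

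| SD | Analysis | r = 0 | r = 0.3 | r = 0.5 | r = 0.7 |
|---|---|---|---|---|---|
| 7.5 | t-test on follow-up | 80% | 80% | 80% | 80% |
| 7.5 | Plan's rule | 80% | 80% | 81% | 82% |
| 7.5 | Change-score t-test | 51% | 66% | 80% | 95% |
| 7.5 | ANCOVA | 78% | 82% | 88% | 97% |
| 16 | t-test on follow-up | 26% | 26% | 26% | 26% |
| 16 | Plan's rule | 26% | 26% | 26% | 26% |
| 16 | Change-score t-test | 15% | 20% | 26% | 40% |
| 16 | ANCOVA | 25% | 27% | 32% | 44% |

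ANCOVA equals the t-test at r of about 0.22. Below that it loses at most about 2 points.

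**6. Conditional behaviour.** At SD 7.5 and r = 0.5, when baseline favours one arm by more than one standard error (7.5 × 0.408 = 3.06), the mean error in the estimate is +2.3 for the t-test, +1.8 for the plan's rule and about 0 for ANCOVA. Overall type I error is about 5% for the t-test and ANCOVA, and 3.7% to 5.1% for the plan's rule. Among trials with a non-significant imbalance above one standard error, the plan's rule has a type I error of about 7% at r = 0.5 and 8.5% at r = 0.7; ANCOVA stays near 5%.

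**The case against.** - **The t-test is valid.** This stands. Over all randomizations it is unbiased with correct error, and the 1.1 to 2.6 mL/min shift at SD 7.5 is below one standard error (3.06). The bias is conditional on the imbalance that occurs, and the remaining loss is one of efficiency.
- **The gain depends on an unknown correlation.** This also stands. At r = 0.3 and SD 7.5 the gain is under 2 points (80.2% to 81.8%). But the covariate is the same measurement on the same patient, and the worst loss is about 2 points.
- **The t-test may be meant on change.** The plan speaks of improvement in renal function and does not rule this out. The sample size paragraph gives SD 7.5 at baseline and 16 after conversion. With that pair, the change score has SD √(7.5² + 16² − 2r × 7.5 × 16), or 15.5 / 13.9 / 12.0 at r = 0.3 / 0.5 / 0.7, and power of 27% / 33% / 42%. ANCOVA gives 27% / 32% / 44%, so in that case it has no real power advantage over a change score. The plan specifies no change score, however, and powers the trial on raw means.
- **Baseline clearance could count as a disease characteristic.** Granted, but the table shows that the rule then recovers almost none of the power.
- **It may be late to change.** Section 6.0 gives a study end date of 1 October 2019, and the approval stamp is 1/7/2020. The documents do not show whether outcome data have been seen, which affects how the change is labelled.

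**Conclusion.** The concern holds, as a worthwhile and nearly free improvement; the planned t-test is not invalid. At 12 per arm and SD 7.5, pre-specified ANCOVA raises power from 80% to between 82% and 97% for r from 0.3 to 0.7, while the significance rule stays at 80% to 82%. About one trial in six would carry an unadjusted baseline imbalance above 0.5 SD.

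The result rests on an assumed r above about 0.22, on eGFR-based SDs standing in for clearance, and on the t-test being applied to follow-up values. If the SD is 16, ANCOVA still reaches only 27% to 44%, so the sample size problem that the plan itself acknowledges remains.

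**What to change.** Replace the analysis paragraph in Section 11.0 with wording such as:

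> The primary analysis is a linear regression (ANCOVA) of 24-hour creatinine clearance at [one of Month 6, 12 or 24, fixed by the sponsor before outcome data are seen] on treatment arm and baseline 24-hour creatinine clearance. The adjusted difference is reported with its 95% confidence interval. No covariate is added because of a baseline significance test. The unadjusted t-test and the Mann-Whitney U test are sensitivity analyses.

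Delete the sentence that makes adjustment depend on a significant baseline difference. If outcome data by arm have already been examined, date the change and report the ANCOVA as added after the fact beside the planned t-test.

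The cost is one paragraph and one degree of freedom, with 1 to 2 points of power lost if the correlation is near zero. No extra patients, visits or measurements are needed.

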#### **Enrollment Exclusion - Randomization**

- Patients who have severe hypercholesterolemia (>350 mg/dL; >9 mmol/L) or hypertriglyceridemia (>500 mg/dL; >8.5 mmol/L) within 6 months of transplantation. Patients with controlled hyperlipidemia are acceptable at the time of randomization.
- Patients with platelet count < 50,000/mm3 at the time of randomization.
- Patients with an absolute neutrophil count of < 1,000/mm^3 or white blood cell count of <2,000/mm^3 at the time of randomization.
- Patients who have tested positive for HIV. Negative laboratory results obtained within 6 months prior to transplant are acceptable.
- Patients with clinically significant systemic infection requiring active use of IV antibiotics at the time of randomization. Patients who are in a critical care setting at the time of randomization requiring life support measures such as mechanical ventilation, dialysis, requirement of vasopressor agents.
- Patients who require renal replacement therapy for clearance within 7 days prior to randomization.
- The presence of thrombosis via Doppler ultrasound of the major hepatic arteries, major hepatic veins, portal vein and inferior vena cava. Results obtained within 5 days prior to randomization are acceptable, however no sooner than Day 25 post-transplantation.
- An episode of acute rejection that required antibody therapy or more than one steroid sensitive episode of acute rejection during the run-in period. This includes patients who have not completed steroid treatment for acute rejection within 7 days prior to randomization.
- Patients with a confirmed spot urine protein-to-creatinine ratio that indicates greater than 0.7 mg protein /mg creatinine. Laboratory results obtained after transplant surgery and within 4 months of randomization are acceptable.
- Use of immunosuppressive agents or treatments after baseline that are not utilized in the protocol.

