#### Side effects of lothalamate clearance test:

Rare allergic reactions to iothalamate in subjects known to be allergic to iodine. Can range from urticaria to anaphylactic shock. Other adverse effects of iothalamate include arrythmias, bradycardia, generalized vasodilation, extravasation of iothalamate during injection, seizures, and weakness of extremities. Abnormal sensation or muscle spasm in the injection site has been reported but in patients being infused with five to thirteen times the amount planned in this study and at a faster infusion rate.

Mycophenolic acid has bone marrow suppression as the main side effect and rarely may have neurotoxicity associated with it. It is also an enteric coated formulation and hence should have less of the GI side effects such as nausea, vomiting and diarrhea, than mycophenolic mofetil which is a similar drug.

Given that arm A will consist of the patients on everolimus and mycophenolic acid, with complete withdrawal of calcineurin inhibitor, there will be a risk of bone marrow suppression and leucopenia, which will be dosage dependent.

Both calcineurin inhibitors and mycophenolic acid increase the patient risk for cancer, especially post transplant lymphoproliferative disease. Everolimus is thought to have an antiproliferative effect and may reduce the risk for the development of cancer.

All patients will be monitored closely for any of the above side effects. Other than the scheduled study clinic visits and testing, allpatients will be followed as per the Penn State Division of Transplantation follow up guidelines. For the first 24 months post liver transplant all our patients undergo the following routine lab collection procedure, the frequency of which may be adjusted based on patient clinical status and need:

Routine/standard of care laboratory tests from post op month 1 through post op month 24 include: :

✓ 1st 5 months postop: 2x/week labs as follows: Sodium, Potassium, Chloride, Bicarbonate level, BUN, Creatinine, Magnesium, Calcium, Phosphorus, CBC, PT, INR, PTT, Liver Function Tests (Total & Direct Bilirubin, AST, ALT, Alkaline Phosphatase & Gamma Glutamyl Transferase), Glucose & Immunosuppressive agent trough levels. Lipid Panel to be performed once a week.

PRAMS00038115 Approval: 1/7/2020

IRB # 38115

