# 14.0 Compensation

For patients randomized into Group A who are receiving Everolimus medication will be reimbursed for travel expenses in order to return twice per week during the first 3 months after randomization to have the Everolimus blood level checked at Hershey Medical Center's Laboratory. The reimbursement for travel expense is 24 cents per mile based on the 2013 Internal Revenue Service standard mileage reimbursement rate for medical travel and the total repayment will not exceed \$300.00. If the patient does not complete the study for any reason during the first 3 months after randomization, the patient will be paid for the medical travel expense up to the time of study discontinuation.

For patients randomized into Group B who are receiving Tacrolimus or Cyclosporin and Mycophenolic acid medications will not receive any payment or compensation for being in this research study because they may continue to have medication blood levels checked at the local laboratory with blood level results faxed to [name] office

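### Safety is compared only through yes/no indicators: no baseline-adjusted comparison on the measured scale is planned for the lipid, blood-count and testosterone values the trial already collects

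*Combined protocol and SAP*

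**What the plan says.** Section 11.0 describes the safety endpoints in two sentences: "Safety endpoints are all binary indicators (discontinuation, change of therapy, hyperlipidemia, etc", and "All of these safety endpoints will be compared between treatment arms using chi-square tests". It gives no threshold, time window or rule for a patient already affected at entry.

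Section 11.0 expects randomization to balance the arms, "so no multivariate analyses are planned". A linear regression is held in reserve if a significant imbalance appears, but that text belongs to the creatinine clearance comparison. The Bonferroni sentence at the end of the analysis text mentions repeated time points and names no safety variable.

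On entry status, the randomization exclusions in Section 4.0 remove only severe lipid values ("Patients who have severe hypercholesterolemia (>350 mg/dL; >9 mmol/L) or hypertriglyceridemia (>500 mg/dL; >8.5 mmol/L) within 6 months of transplantation") and then state "Patients with controlled hyperlipidemia are acceptable at the time of randomization".

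On data, Section 7.0 gives every patient the same routine laboratory schedule to month 24. Blood counts are twice weekly in the first 5 months, with lipids weekly ("Lipid Panel to be performed once a week"). Both are then weekly to month 12 and every two weeks after that. Section 6.0 adds "Testosterone levels" to the tests at the study visits (Baseline, Months 6, 12 and 24).

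**The concern.** Section 7.0 names raised lipids, low blood counts and low testosterone as everolimus concerns. They are measured on a continuous scale, and a pre-treatment value is available or easily taken. A yes/no split ignores how far a value moved and where the patient started. In a 24-patient pilot those are the main sources of precision.

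The second strand is entry status. Some patients may be randomized with hyperlipidemia. For cholesterol, the exclusion limit is above 9 mmol/L, while the everolimus dose-reduction table in Section 7.0 starts at 8 mmol/L. The numerical limit therefore does not keep out a patient between the two. If such patients were counted as events in both arms, the arms would look more alike than the drug effect makes them.

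At stake is whether the pilot yields a usable estimate of Arm A's laboratory toxicity. The primary renal comparison is not affected.

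**Working it through.** **Inputs from the documents.** 12 per arm (Section 4.0); two-sided alpha 0.05, difference 9.0, SD 7.5 (Section 11.0, sample size). No safety rate, SD, entry prevalence or baseline correlation is given, so those below are assumptions.

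**1. The plan's own figure.** Standardized difference d = 9.0/7.5 = 1.2. Noncentrality = d·√(n/2) = 1.2·√6 = 2.94 on 22 df. Power = 80.2%, which agrees with the stated 80%. This concerns renal function. I borrow d = 1.2 only as a familiar scale.

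**2. Cost of the yes/no split.** Assume a normal laboratory value shifted by d SDs in Arm A. A cut at c SDs above the Arm B mean gives event rates 1−Φ(c) and 1−Φ(c−d). Power comes from enumerating all 2×2 tables with 12 per arm, using uncorrected chi-square at p<0.05.

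For d = 1.2:
- c = 0.6 (best cut): 27.4% v 72.6%, power 67% (Fisher 50%).
- c = 1.0: 15.9% v 57.9%, power 62%.
- c = 1.5: 6.7% v 38.2%, power 45%.

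ANCOVA on the Baseline value multiplies the SD by √(1−ρ²). With ρ = 0.5, the effective d is 1.2/√0.75 = 1.386, noncentrality 3.39, power 90%.

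| Assumed shift (SD) | Chi-square, cut midway | t-test | ANCOVA, ρ=0.5 | ANCOVA, ρ=0.7 |
|---|---|---|---|---|
| 0.8 | 38% | 47% | 58% | 75% |
| 1.0 | 53% | 65% | 77% | 91% |
| 1.2 | 67% | 80% | 90% | 98% |

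**3. Multiplicity.** Section 11.0 applies Bonferroni to repeated time points. At 0.05/3 = 0.0167 and d = 1.2: chi-square 50%, t-test 64%, ANCOVA (ρ=0.5) 78%. At 0.05/18 = 0.0028 (six analytes, three visits): 18%, 36% and 52%.

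**4. Dilution, if entry cases were counted.** Let a fraction π be affected at entry in both arms, and let new onset among the rest be 10% v 50% (assumed). Each arm's rate is π + (1−π)·incidence, so the risk difference is 0.40·(1−π).

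| π | Rates | Difference | Chi-square power |
|---|---|---|---|
| 0 | 10% v 50% | 0.40 | 60% |
| 0.1 | 19% v 55% | 0.36 | 48% |
| 0.2 | 28% v 60% | 0.32 | 40% |
| 0.3 | 37% v 65% | 0.28 | 32% |
| 0.4 | 46% v 70% | 0.24 | 25% |
| 0.5 | 55% v 75% | 0.20 | 19% |

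**The case against.** The strongest reply is that a binary toxicity comparison is a reasonable choice for a 24-patient pilot, and that the measured scale has faults of its own.

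- Section 7.0 treats raised lipids with statins and low neutrophils with filgrastim before everolimus is reduced. Values at fixed visits would be pulled toward normal, while a yes/no record over the whole period still captures the event. This stands.
- Section 10.0 lists refractory laboratory toxicity as grounds for removal, so the worst cases may be missing at later visits. This also stands. Both are reasons to keep the binary endpoints and read the two together.
- More models mean more tests. One binary test over the whole follow-up needs no correction for visits. Its 67% compares with 78% for ANCOVA corrected for three visits, but with 52% if all 18 tests are corrected. The added analysis should therefore be supportive and reported as estimates.

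Three stronger readings are tempting, and the documents do not support them.

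- A reader might infer that hyperlipidemia present at entry counts as an event. No section says so. The evaluation schedule records adverse events from Baseline, but no rule ties that to this endpoint.
- A reader might infer that the repeated values go unused. They drive dose changes (Section 7.0), patient removal and weekly review (Section 10.0), and the DSMB reviews progress reports every six months (Section 13.0). What is missing is a planned between-arm comparison. Blood counts and testosterone are not named in Section 11.0, so they lack a stated analysis and are not shown to be dichotomized.
- A reader might infer from Section 14.0 that Arm A is tested more intensively, since of Arm B patients it says "they may continue to have medication blood levels checked at the local laboratory". That text concerns where drug levels are drawn and who is paid for travel. Section 6.0 sets one trough-level frequency for both drug classes, and Section 7.0 gives all patients the same routine lipids and blood counts, adjustable by clinical need.

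**Conclusion.** The concern holds in a limited form. Section 11.0 commits every safety endpoint to a yes/no indicator and plans no baseline-adjusted comparison of laboratory values that are already collected. At an assumed 1.2 SD shift with 12 per arm, power is at most 67% for chi-square, 80% for a t-test and about 90% for ANCOVA at ρ = 0.5. The ordering is the same at 0.8 and 1.0 SD.

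The figures assume normal values, complete data and a correlation the documents do not give. They do not carry over to testosterone in men only, where there will be fewer patients.

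The dilution result is conditional: it applies only if entry cases are counted, and the plan is silent on that. The silence alone is missing detail. The absent measured-scale analysis is the more consequential gap and is cheap to close. Nothing here shows the trial's stated sample size to be wrong.

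**What to change.** In Section 11.0, after the safety sentences, add text to this effect:

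> Binary safety endpoints are assessed over the whole follow-up. Hyperlipidemia and other laboratory toxicities count only when new, or worsened, relative to the Baseline value. In addition, cholesterol, triglycerides, platelets, hemoglobin, ANC and testosterone (men) at Months 6, 12 and 24 are compared between arms by ANCOVA on the Baseline value, reported as estimates with 95% confidence intervals and treated as supportive. Use of lipid-lowering therapy and of filgrastim is reported by arm beside these estimates.

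The study team should also state which pre-randomization measurement serves as Baseline for the routine laboratory values, and what counts as worsened.

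The cost is SAP wording and a few extra models, with no new procedures. The limitation is that measured values are affected by lipid-lowering therapy and filgrastim and by the removal of patients for toxicity, so they must be read together with the binary endpoints. The binary endpoints should not be restricted to the scheduled visits, since that would drop real events between visits from the comparison.
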